Reference: Internal Clinical Pharmacology Drug-drug interaction (DDI) memo, updated Oct. 2, 2011, 29-Oct-2012 which summarizes DDI data from three sources including the FDA's "Guidance for Industry, Drug Interaction Studies", the University of Washington's Drug Interaction Database, and Indiana University School of Medicine's Drug Interaction Table.

Addendum 4: Dose Modifications for abnormal serum drug concentrations without grade III/IV toxicities, grade \geq III toxicities (CTCAE version 4.0) except for stomatitis and lipid/hyperglycemia toxicities

- Patient will have regularly scheduled everolimus levels drawn throughout the study
- Everolimus is available in 2.5mg, 5mg and 10mg strengths
- The reference range for patients experiencing a <II common toxicity (CTCAE version 4.0) is 3-15ng/mL
- Anytime a dose is adjusted, repeat everolimus serum trough levels will be re-drawn 14 days (\pm 3 days) later. As clinically possible, all patients' other labs will be reset to match this new everolimus serum trough level schedule.
- Once everolimus is held due to high serum trough levels, everolimus should be held for 7 days before restarting at a lower dose level.
- During a treatment hold, everolimus levels will not be drawn once the serum trough level is less than 1.0.
- There is no limit on how long a patient can be on everolimus treatment hold. Labs will be monitored every two weeks while the patient is on hold.
- For patients >15 ng/mL or <3.0 ng/mL and not experiencing >II grade common toxicity, their dose will be adjusted by $+/-.2.5$ mg/day; lowest dose allowed is 2.5mg every 4 days. The study nurse will provide a calendar to patients when the dose level is 2.5 mg taken every 3 or 4 days
- If a patient on a schedule of 2.5 mg (QOD) or lower misses a dose, that dose should be made up.
- Non-hematologic grade \geq III CTCAE toxicities: hold drug until CTCAE toxicity is (I) but can be continued at grade 2 if the baseline values were within the range of grade 2 and restart at a dose level -2.5mg/day. Lowest dose allowed is 2.5mg every 4 days
- Grade 4 or 4 clinical failure – discontinue RAD001
- Recurrence of grade 4 toxicity after dose reduction – discontinue RAD001
- Hematologic grade \geq III CTCAE toxicity
 - Anemia
 - Hgb <8.0 g/dL: transfuse RBC; hold drug for 7 days or until Hgb >10 mg/dL (untransfused): whichever is longer. Restart at a dose - 2.5mg/day. Lowest dose allowed is 2.5mg every 4 days
 - Thrombocytopenia

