Treatment of hyperlipidemia should take into account the pre-treatment status and dietary habits. Blood tests to monitor hyperlipidemia must be taken in the fasting state. Hyperlipidemia and hypertriglyceridemia should be treated according to local best clinical practice. Patients should be monitored clinically and through serum chemistry for the development of rhabdomyolysis and other adverse events as required in the product label/data sheets for HMG-CoA reductase inhibitors.

Management of hyperlipidemia and hyperglycemia

Adverse Drug Reaction	Severity	Afinitor Dose Adjustment and Management Recommendations
Metabolic events (e.g. hyperglycemia, dyslipidemia)	Grade 1	No dose adjustment required. Initiate appropriate medical therapy and monitor.
	Grade 2	No dose adjustment required. Manage with appropriate medical therapy and monitor.
	Grade 3	Temporary dose interruption. Re-initiate Afinitor at lower dose. Manage with appropriate medical therapy and monitor.
	Grade 4	Discontinue Afinitor and treat with appropriate medical therapy.

Dyslipidemia (including hypercholesterolemia and hypertriglyceridemia) has been reported in patients taking everolimus. Monitoring of blood cholesterol and triglycerides prior to the start of everolimus therapy and periodically thereafter as well as management with appropriate medical therapy is recommended.

Hyperglycemia has been reported in patients taking everolimus. Monitoring of fasting serum glucose is recommended prior to the start of everolimus therapy and periodically thereafter. More frequent monitoring is recommended when everolimus is co-administered with other drugs that may induce hyperglycemia. Optimal glycemic control should be achieved before starting trial therapy.

Addendum 7: Management of non-infectious pneumonitis

Non-infectious pneumonitis is a class effect of rapamycin derivatives. Cases of non-infectious pneumonitis (including interstitial lung disease) have also been described in patients taking everolimus. Some of these have been severe and on rare occasions, a fatal outcome was observed.

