Grade 2 (Symptomatic, not interfering with Activities of Daily Living)	CT scan with lung windows. Consider pulmonary function testing includes: spirometry, DLCO, and room air O ₂ saturation at rest. Consider a bronchoscopy with biopsy and/or BAL. Monitoring at each visit until return to \leq grade 1. Return to initial monitoring frequency if no recurrence.	Symptomatic only. Consider corticosteroids and/or other supportive therapy if symptoms are troublesome.	Rule out infection and consider interruption of Everolimus until symptoms improve to Grade \leq 1. Re-initiate Everolimus at one dose level lower. Discontinue Everolimus if failure to recover within \leq 28 days.
Grade 3 (Symptomatic, Interfering with Activities of Daily Living. O ₂ indicated)	CT scan with lung windows and pulmonary function testing includes: spirometry, DLCO, and room air O ₂ saturation at rest. Monitoring at each visit until return to \leq grade 1. Return to initial monitoring frequency if no recurrence. Bronchoscopy with biopsy and/or BAL is recommended.	Consider corticosteroids if infective origin is ruled out. Taper as medically indicated.	Rule out infection and interrupt Everolimus until symptoms improve to Grade \leq 1. Consider re-initiating Everolimus at one dose level lower (approximately 50% lower than the dose previously administered depending on individual clinical circumstances) Discontinue Everolimus if failure to recover within \leq 28 days. If toxicity recurs at Grade 3, consider discontinuation
Grade 4 (Life-threatening, ventilatory support indicated)	CT scan with lung windows and required pulmonary function testing, if possible, includes: spirometry, DLCO, and room air O ₂ saturation at rest. Monitoring at each visit until return to \leq grade 1. Return to initial monitoring frequency if no recurrence. Bronchoscopy with biopsy and/or BAL is recommended if possible.	Consider corticosteroids if infective origin is ruled out. Taper as medically indicated.	Rule out infection and discontinue Everolimus.

Addendum 8: Action to be taken for positive baseline hepatitis B results

Test	Result	Result	Result	Result	Result
HBV-DNA	+	+ or -	-	-	-
HBsAg	+ or -	+	-	-	-
HBsAb	+ or -	+ or -	+ and no prior HBV vaccination	+ or -	- or + with prior HBV vaccination
HBcAb	+ or -	+ or -	+ or -	+	-

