Recommendation	Prophylaxis treatment should be started 1-2 weeks prior to first dose of study drug. Monitor HBV-DNA approximately every 4 weeks		No prophylaxis Monitor HBV-DNA approximately every 4 weeks		No specific action

Antiviral prophylaxis therapy should continue for at least 4 weeks after last dose of study drug.

For patients who have already received study drug prior to the approval of Protocol Version date February 18, 2014, HBV-DNA testing will be performed at the patient's next visit, and the result will be regarded as baseline. Any action for positive hepatitis results will then proceed as detailed in the table above.

Addendum 9: Guidelines for management of hepatitis B

HBV reactivation (with or without clinical signs and symptoms)*	

For patients with baseline results:
 
Positive HBV-DNA OR positive HBsAg
 
-----
 
reactivation is defined as: [Increase of 1 log in HBV-DNA relative to baseline HBV-DNA value OR new appearance of measurable HBV-DNA]
 
AND
 
ALT elevation x 5 ULN
	
Treat: Start a second antiviral AND Interrupt study drug administration until resolution: \leq grade 1 ALT (or baseline ALT, if $>$ grade 1) and \leq baseline HBV-DNA levels
 
If resolution occurs within \leq 28 days study drug should be re-started at one dose lower, if available. If the patient is already receiving the lowest dose of study drug according to the protocol, the patient should restart at the same dose after resolution. Both antiviral therapies should continue at least 4 weeks after last dose of study drug.
 
If resolution occurs $>$ 28 days Patients should discontinue study drug but continue both antiviral therapies at least 4 weeks after last dose of study drug.

For patients with baseline results:
 
Negative HBV-DNA and HBsAg AND Positive HBs Ab (with no prior history of vaccination against HBV), OR positive HBc Ab
 
-----
 
reactivation is defined as: New appearance of measurable HBV-DNA
	
Treat : Start first antiviral medication AND Interrupt study drug administration until resolution: \leq baseline HBV-DNA levels
 
If resolution occurs within \leq 28 days study drug should be re-started at one dose lower, if available. If the patient is already receiving the lowest dose of study drug according to the protocol, the patient should restart at the same dose after resolution. Antiviral therapy should continue at least 4 weeks after last dose of study drug.

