If resolution occurs > 28 days Patients should discontinue study drug but continue antiviral therapy at least 4 weeks after last dose of study drug.

- * All reactivations of hepatitis B are to be recorded as grade 3 (CTCAE v 3.0 Metabolic Laboratory/Other: Viral Re-activation), unless considered life threatening by the investigator; in which case they should be recorded as grade 4 (CTCAE v 3.0 Metabolic Laboratory/Other: Viral Re-activation). Date of viral reactivation is the date on which **both** DNA and ALT criteria were met (e.g. for a patient who was HBV-DNA positive on 01-JAN-10 and whose ALT reached $\geq 5 \times$ ULN on 01-APR-10, the date of viral reactivation is 01-APR-10).

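### Addenda 4 and 9 are not reconciled for hepatitis B reactivation: Addendum 9 gives reactivations recorded as grade 4 no action of their own, and the two addenda conflict at the lowest everolimus dose

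*Combined protocol and SAP*

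**What the plan says.** **Addendum 9 (hepatitis B management).** The table is headed "HBV reactivation (with or without clinical signs and symptoms", so it covers all reactivations. It has two rows, split by baseline hepatitis B results. Each row interrupts everolimus, starts an antiviral (a second one in the first row), and then branches on time to resolution. If resolution comes within 28 days, "study drug should be re-started at one dose lower, if available". For a patient already on the lowest protocol dose, "the patient should restart at the same dose after resolution". If resolution takes longer than 28 days, the drug is discontinued. The footnote assigns grade 3 to every reactivation "unless considered life threatening by the investigator; in which case they should be recorded as grade 4". Neither row refers to that grade.

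**Addendum 4 (dose modifications).** Its heading covers toxicities of grade III or higher and excepts only stomatitis and lipid or glucose toxicities. Four of its rules could reach a reactivation:
- a line reading "Grade 4 or 4 clinical failure", followed by an instruction to discontinue;
- a line discontinuing when grade 4 toxicity recurs after a dose reduction;
- a rule for non-hematologic toxicity of grade III or higher, which holds the drug and restarts it 2.5 mg/day lower;
- a closing rule that takes the patient off study if toxicity above grade II occurs on the lowest dose, 2.5 mg every 4 days.

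**Addenda 5 to 7 (stomatitis, metabolic events, pneumonitis).** Each has a separate grade 4 row. Addenda 5 and 6 say "Discontinue Afinitor and treat with appropriate medical therapy". Addendum 7 says "Rule out infection and discontinue Everolimus".

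**Pointers.** Section 3.2.5 refers the reader to Addendum 9 for the definition and management of reactivation. Footnote 6 of the study calendar refers to Addenda 8 and 9.

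**The concern.** Addendum 9 separates life-threatening reactivations from the rest by grade and then makes no use of the distinction when it decides whether everolimus is resumed. Addendum 4, which on its face also covers these events, does attach consequences to grade. The two addenda do not refer to each other, and no ranking between them is stated.

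A treating physician with such a patient could therefore find one instruction in Addendum 9 and a different one in Addendum 4, and could follow either while believing that the protocol had been observed. What is at stake is whether a patient is re-exposed to an immunosuppressive drug or stopped permanently after a reactivation, and whether like patients are handled alike. Section 3.2.5 reports reactivation with everolimus and says that some infections were severe and occasionally fatal. Patients with hepatitis B core antibody and normal transaminases are eligible, so the situation is foreseeable.

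**Working it through.** No arithmetic applies. The check sets the addenda side by side for reactivations that resolve within 28 days, since that is where Addendum 9 says to resume the drug.

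| Reactivation resolving within 28 days | Addendum 9 | Addendum 4 | Result |
|---|---|---|---|
| Grade 3, above the lowest dose | Resume one dose lower | Hold, then restart 2.5 mg/day lower | Same direction |
| Grade 4, above the lowest dose | Resume one dose lower | Discontinue, on the grade 4 line; or hold and restart lower, on the non-hematologic line | Depends on how Addendum 4 is read |
| Grade 3 or 4, at the lowest dose | Resume the same dose | Off study | Opposite |

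1. *Does Addendum 9 have a grade 4 class?* Yes, in its footnote.

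2. *Does its restart rule treat that class differently?* No. Time to resolution is the only branch point in both rows. The verb for restarting is directive, not permissive.

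3. *Does Addendum 4 reach these events?* By its heading, yes. Hepatitis B is not among the exceptions, and the footnote makes every reactivation grade 3 or 4.

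4. *What does Addendum 4 say at grade 4?* It is not uniform. The discontinuation line is garbled and its scope is unclear. The recurrence line presupposes that a patient may have been restarted after a first grade 4 event. The non-hematologic rule starts at grade III and has no upper limit, so it includes grade 4. Even the most severe platelet tier (below 10,000) restarts at a lower dose. The second row of the table is therefore an ambiguity, not a proven contradiction.

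5. *What does it say at the lowest dose?* Here it is clear: toxicity above grade II takes the patient off study. Addendum 9 is equally clear that a patient on the lowest dose resumes that dose. Since no reactivation is recorded below grade 3, every reactivation at that dose that resolves in time falls under both instructions. This conflict does not depend on the garbled line.

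6. *What do Addenda 5 to 7 add?* They govern other events and cannot conflict with Addendum 9. They show only that, elsewhere in this protocol, grade 4 gets its own action. Addendum 7 is the most telling: it uses a 28-day recovery limit at grades 2 and 3 and still keeps a separate grade 4 row. So a 28-day limit does not, in this protocol, stand in for a grade 4 action.

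7. *Do the pointers settle precedence?* Section 3.2.5 and calendar footnote 6 tell the reader where reactivation is managed. Neither says that Addendum 4 ceases to apply.

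**The case against.** The strongest reply is that Addendum 9 is the specific rule and the protocol sends the reader there. Section 3.2.5 also describes Addenda 4 to 7 separately, as recommendations for suspected drug toxicities. On that view the specific rule prevails and nothing conflicts. This is a reasonable reading and may be what was intended, but it has to be inferred. Addendum 4's heading lists its exceptions by name and hepatitis B is not one of them.

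A second reply is that the footnote is only a recording convention. It cites CTCAE version 3.0, whereas Addendum 4 uses version 4.0, and nothing says that the assigned grade is meant to trigger Addendum 4. That is correct. Equally, nothing says that it is not, and Addendum 4's triggers are stated in terms of grade.

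Third, there are safeguards. Restart requires hepatitis B DNA to be at or below baseline, and in the first row ALT must also have recovered; antiviral treatment is added in both rows. Section 3.2.3 allows removal for a reaction that is serious or cannot be tolerated, and Section 3.2.5 asks the physician to consider stopping when infection is diagnosed. These reduce the risk, but the last two are discretionary and do not displace a directive to restart.

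Four stronger inferences are tempting, and the documents do not support them:
- *Addendum 4 discontinues at every grade 4 toxicity.* Its hold-and-restart and recurrence lines point the other way.
- *Every grade 4 reactivation gets opposite instructions.* Above the lowest dose this depends on one reading of a defective line.
- *Addenda 5 to 7 contradict Addendum 9.* They cover different events.
- *The safety results would shift by a calculable amount.* No reactivation rate is given. A reactivation recorded as grade 3 or 4 enters the proportion with grade 3 or higher toxicity whether or not the drug is resumed, and an unexpected hospitalization already counts as a failure under Section 6.0.

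**Conclusion.** The point stands in a limited form. Addendum 9 gives no separate action for reactivations that it records as grade 4, and its relation to Addendum 4 is unstated. Above the lowest dose the result is an ambiguity, because Addendum 4 is itself unclear at grade 4. At the lowest dose the two addenda give opposite instructions for any reactivation that resolves within 28 days.

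The size cannot be put as a number. The documents give no expected frequency, Section 3.2.5 calls reactivation with everolimus sporadic, and patients positive for surface antigen are excluded, which narrows the first row of Addendum 9. The event should be rare. The reason to act is patient safety and consistent conduct, not the precision of an endpoint.

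The conclusion assumes that Addendum 4's heading means what it says about scope, that the grade assigned in Addendum 9's footnote counts as a toxicity grade for Addendum 4, and that the lowest protocol dose in Addendum 9 is the one named in Addendum 4. If the sponsor intended otherwise on any of these, one sentence saying so would settle the matter. No view is taken on which clinical action is right.

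**What to change.** Reconcile Addenda 4 and 9 in one of two ways:

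- State which addendum governs hepatitis B reactivation, and in both rows of Addendum 9 give an explicit action for reactivations recorded as grade 4 and for those at the lowest dose, consistent with Addendum 4.
- Or add hepatitis B reactivation to the exceptions in Addendum 4's heading, so that Addendum 9 alone applies, with its action for grade 4 and for the lowest dose stated there.

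The sponsor decides the clinical action in each case. Clarifying the garbled grade 4 line in Addendum 4 would help, but is not enough alone: the restart instruction in Addendum 9 and the lowest-dose conflict would remain.

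The cost is a line or two at the next amendment. It needs no new procedures, visits or data.
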